Prior to enrolling on this trial participants will have already made a decision to convert to buprenorphine therapy after lengthy discussions with the clinical care team. That discussion includes risks and benefits of buprenorphine and the need to be in mild- moderate withdrawal prior to initiating buprenorphine. In addition, most patients will be weaned down as much as possible from their current opioid dose prior to initiating the protocol below.

- a. Study design, including the sequence and timing of study procedures.
 1. **Within 90 days prior to day 0** subject will sign Informed Consent Form (ICF) (R) , have urine toxicology testing, and complete HRQoL tool (ASCQ-Me) (R),brief pain inventory (BPI) (R), the PROMIS Pain Interference – Short Form instrument (R), and the PROMIS Physical Function – Short Form instrument (R). The ASCQ-Me tool is a validated health related quality tool for use specifically in SCD. The PROMIS Pain Interference instrument measures the degree to which pain hinders social engagement and life enjoyment. The PROMIS Physical Function instrument measures the degree to which pain affects everyday physical activities.
 2. Data will be collected on acute care utilization, sickle cell disease co-morbidities from chart abstraction and recorded in case report forms.
 3. **Day 0:**
 - a. Subject will complete ASCQ-Me, PROMIS Pain Interference, PROMIS Physical Function, and BPI with 7 day anchor (R).
 - b. Prior to discharge from SCIC subject will have COWS assessment, pain rating collected.
 4. **Day 1:** Subject will return to repeat COWS.
 5. Subject will return **day 14, day 30, day 90, and day 180** to repeat ASCQ-Me, PROMIS Pain Interference, PROMIS Physical Function, and BPI (R), or subject will complete these surveys over the phone or online on those days in lieu of coming for a study visit. Acute care utilization will be collected from subject, medical record and Crisp.

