- a. The only change in the ICF version approved by IRB on November 6 2019 was the option of completing the study surveys remotely (over the phone or online) for participants. Patients that were consented using a previous version of the ICF and are enrolled to the study before the November version, have agreed to all study procedures, but have not agreed to having the option to complete the study surveys online or over the phone. The study team will reach out to these **currently enrolled patients** during in-person clinical visits, via telemedicine appointments or over the phone to re-consent them to the study in-person or remotely using the ICF version approved on November 6 2019. On the instances when the re-consent process is done remotely, the person obtaining the re-consent will:
 - i. Sign, print their name, and add date and time of the re-consent, under the consent line.
 - ii. Add on the line of the patient signature: *[First and Last name of patient]* provided verbal affirmation of this newer version of their previously signed consent (the only change from previous signed version by patient is that the surveys can be completed remotely).
- 6. Data will be extracted from EPIC and CRISP on health care utilization for the 6 months prior to enrollment and 3 years post conversion.
- 7. We will also collect data on the 15-20 patients that we have now converted to buprenorphine. We will retrospectively review charts to collect genotype data, acute care utilization (ED, sickle infusion clinic and hospitalizations), COWS scores, sex, age and any complications that occurred with conversion. These subjects will be asked to complete ASCQ-Me and Promis tools.
- b. (distinguish research procedures from those that are part of routine care).
All research activities are noted with (R) above.
- c. Study duration and number of study visits required of research participants.
Each participant will be enrolled for 3 years and will have up to 6 study visits with the possibility of completing the ASCQ-Me, BPI and Promis tools over the phone or online instead of coming in for a study visit. The initial visit is part of routine care that we provide for conversion from opioids to buprenorphine.
- d. Blinding, including justification for blinding or not blinding the trial, if applicable. NA
- e. Justification of why participants will not receive routine care or will have current therapy stopped.
NA
- f. Justification for inclusion of a placebo or non-treatment group. NA

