- g. Definition of treatment failure or participant removal criteria. NA
- h. Description of what happens to participants receiving therapy when study ends or if a participant's participation in the study ends prematurely.
NA this is an observational trial.

5. Inclusion/Exclusion Criteria

a. Inclusion Criteria:

1. Has SCD, any genotype
2. Is being converted from full agonist opioid therapy to buprenorphine.
3. Able to provide consent
4. Is between the ages 18 and 100.

b. Exclusion Criteria:

1. Unwilling to sign consent.
2. Medical disorder, condition, or history that in the investigator's judgement would impair the patient's ability to participate or complete this study or render the patient to be inappropriate for enrollment.

6. Drugs/ Substances/ Devices

- a. The rationale for choosing the drug and dose or for choosing the device to be used.
NA
- b. Justification and safety information if FDA approved drugs will be administered for non-FDA approved indications or if doses or routes of administration or participant populations are changed. NA
- c. Justification and safety information if non-FDA approved drugs without an IND will be administered. NA

7. Study Statistics

- a. Primary outcome variable.
Primary Endpoint: This will be a descriptive study assessing the safety and benefit of converting subjects from full agonist opioids to buprenorphine. Data will be collected on need for hospitalization within 72 hours of conversion due to withdrawal induced VOC, as well as average COWS scores.
- b. Secondary outcome variables.
Secondary Endpoint: Measurement of quality of life and decreased pain measured by the BPI, ASCQ-Me, PROMIS Pain Interference, PROMIS Physical Function and decreased acute care utilization.
- c. Statistical plan including sample size justification and interim data analysis.
Descriptive study: Paired t-test will be used to compare patient's results on surveys and acute care utilization pre- and post- conversion.
- d. Early stopping rules.
NA

8. Risks

- a. Medical risks, listing all procedures, their major and minor risks and expected frequency.
- b. Participants may feel uncomfortable filling out surveys. Steps taken to minimize the risks.
Participants can stop filling out surveys at any time.
- c. Plan for reporting unanticipated problems or study deviations.
All study deviations and adverse events will be reported to the IRB.
- d. Legal risks such as the risks that would be associated with breach of confidentiality. NA

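### Surveys taken at six times are to be compared by an unspecified paired t-test; name one contrast and estimate it from a repeated-measures model that uses all surveys

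*Combined protocol and SAP*

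**What the plan says.** Section 7c, which is headed as the statistical plan, describes the study as descriptive and then states: "Paired t-test will be used to compare patient's results on surveys and acute care utilization pre- and post- conversion". It names no baseline survey, follow-up survey, lead scale, significance level or rule for missing surveys.

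The study design part of the procedures section schedules the ASCQ-Me, BPI, PROMIS Pain Interference and PROMIS Physical Function six times in the prospective cohort:
- within 90 days before day 0 (item 1);
- on day 0, where the text attaches a 7-day anchor at least to the BPI (item 3a);
- on days 14, 30, 90 and 180 (item 5).

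The opening paragraph of the same section says that "most patients will be weaned down as much as possible from their current opioid dose prior to initiating the protocol below", and refers to "the need to be in mild- moderate withdrawal prior to initiating buprenorphine".

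On completeness, section 8b says "Participants can stop filling out surveys at any time". Item 5a says that patients on earlier consent forms "have not agreed to having the option to complete the study surveys online or over the phone" until they are re-consented. Against that, item 5 lets a visit be replaced: "subject will complete these surveys over the phone or online on those days in lieu of coming for a study visit". Section 10 pays $20 for each follow-up visit outside usual care.

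Item 6 collects utilization for 6 months before enrollment and 3 years after conversion. Item 7 asks the 15-20 already converted patients for ASCQ-Me and PROMIS surveys; no pre-conversion survey is planned for them.

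**The concern.** A paired t-test needs one value before and one value after. With six surveys per patient, someone must decide which two are meant, or how several are combined, and the plan does not say. Three things follow.

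First, if one follow-up is picked, a patient who completed days 14, 30 and 90 but missed day 180 adds nothing to a day-180 test. The study collects those surveys and the plan gives them no stated use. Precision is lost, and if dropout is related to scores the remaining pairs may not represent the cohort.

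Second, the pair can be chosen after the results are seen.

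Third, the choice of baseline may matter. Most patients are weaned before the protocol starts, and withdrawal is needed before buprenorphine is begun. A day-0 score may therefore differ from the screening score, and the apparent change with it.

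The same sentence applies a paired comparison to utilization, where the two windows have different lengths.

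**Working it through.** The plan states no figure to reproduce. The prospective sample size, survey SD, correlations, dropout rate, effect size and significance level are all absent, so everything below except steps 1 and 6 is illustrative.

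**1. Number of pairs (from the schedule).** 2 baselines × 4 follow-ups = 8 per instrument; over four instruments, 8 × 4 = 32.

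**2. Precision.** Assumptions: SD σ = 10, screening at day −45, contrast day 180 minus day 0, random dropout in equal steps over the four follow-ups to a missing fraction d of 20% or 40% at day 180. Three correlation structures:
- C: 0.6 throughout.
- D: 0.5 + 0.5·exp(−days/60), which is 0.525 between day 0 and day 180.
- B: 0.7 within a period and 0.4 across conversion, so that patients differ in response.

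Complete pairs: n × variance = 2σ²(1 − ρ)/(1 − d). For C at 40% this is 2 × 100 × 0.4/0.6 = 133.3.

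All-visit model with time as a category: n × variance = c′(Σ pₖ Xₖ′Vₖ⁻¹Xₖ)⁻¹c, where pₖ is the share of patients with dropout pattern k.

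| Structure | Missing | Pairs | Model | Ratio |
|---|---|---|---|---|
| C | 20% | 100.0 | 92.5 | 1.08 |
| C | 40% | 133.3 | 113.1 | 1.18 |
| D | 20% | 118.8 | 111.1 | 1.07 |
| D | 40% | 158.4 | 137.5 | 1.15 |
| B | 20% | 150.0 | 132.7 | 1.13 |
| B | 40% | 200.0 | 152.4 | 1.31 |

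Without the screening survey the lowest ratios are 1.06 and 1.14. In standard errors: √1.06 to √1.13 is 3-6% larger at 20% missing, and √1.14 to √1.31 is 7-14% larger at 40%.

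Simulated power for a true change of −5, using a random intercept with patient-level jackknife standard errors, exceeds that of the paired t-test by 1-4 points at n = 20. At n = 40 it does so by 2-4 points (20% missing) and 4-9 points (40% missing).

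**3. Bias at 40% missing.** Assumptions: true change −5 (lower is better), structures C and D, dropout odds doubling per 10 points.

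| Dropout follows | Complete pairs | Model |
|---|---|---|
| Previous raw score | −4.2 to −4.7 | −5.0 |
| Worsening since day 0, as last observed | −5.7 to −5.9 | −5.0 |
| Unseen raw score | −4.9 to −5.3 | −5.6 to −5.8 |
| Unseen worsening | −6.4 to −6.6 | −5.6 to −5.8 |

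Timing matters too. If only day 180 is at risk and missingness depends on the day-90 raw score, complete pairs give −4.99 to −5.02, which is no bias. If dropout on the raw score starts only after day 14, they give −4.98 under C and −4.37 under D.

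**4. Complete data.** With every survey present, the model's estimated change equals the mean paired difference, so there is no gain in the estimate.

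**5. Pair left open.** Eight independent tests at an assumed 5% level would give 1 − 0.95⁸ = 34%. Allowing for correlation, with no true change, simulation gives about 25-27% under C and D and 19-20% under B for at least one significant pair per instrument.

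**6. Utilization.** 36 months/6 months = 6. At an unchanged rate the 3-year total is six times the 6-month total, so raw totals cannot be compared.

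**The case against.** **The loss of patients is conditional.** Section 7c does not say that one follow-up will be used. A test at each visit drops no one who has that visit's pair. A paired t-test on each patient's mean available follow-up keeps anyone with one follow-up: about 88% in a simulation at n = 20 with 40% missing at day 180. This stands, and the point is worded accordingly. But the plan adopts neither reading. If change is gradual, a mean of whatever is available also mixes early and late visits differently for different patients.

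**The model is not uniformly safer.** If patients stop because of how they feel at the missed survey, the third row of the bias table applies and the model overstates benefit more than complete pairs do. The documents give no ground for preferring one dropout mechanism. This stands, and it is why the paired result and a sensitivity analysis belong beside the model.

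**The gains are modest and rest on assumed inputs.** This stands. Larger power gains appear with Kenward-Roger degrees of freedom, but part of them comes from the extra degrees of freedom, which rely on an adequate covariance. An elaborate covariance may not fit in a small cohort.

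**Missingness is already addressed in part.** Remote surveys, active re-consent and payment all help, and gaps due to the older consent form may be unrelated to scores. The permission to stop is a risk-minimization statement and forecasts no dropout rate. These points lower the likely size, but they supply no rule for the surveys that are still missing.

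**The study is descriptive.** The same sentence nevertheless commits to a test, and a descriptive estimate also needs a defined contrast. The 5% level is an assumption.

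**Conclusion.** The point holds as a cheap improvement. Six scheduled surveys per instrument and an unspecified paired t-test leave 8 pairs open, and any single-visit pair discards patients who lack that visit. Naming one contrast and using all surveys costs little. Under the assumptions in the working (SD 10, correlations 0.4-0.7, 20-40% missing at day 180), it avoids a variance inflation of about 6-13% at 20% missing and 14-31% at 40%. It also closes a choice that carries a 19-27% chance of a spurious result per instrument at an assumed 5% level.

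A reader might infer more, and the documents do not support it:
- That the plan has chosen day 180 and will drop patients: no follow-up is named.
- That the paired results will be biased and the model will correct them: no dropout rate or mechanism is given, and the answer can go either way.
- That the pair will be picked for its result: the plan leaves this open but does not say so.
- That the study's main conclusion is at risk: surveys are secondary, and the primary safety endpoint is untouched.

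**What to change.** For the prospective cohort, add to section 7c:
- One baseline (screening or day 0), one lead scale per instrument, and one main contrast, for example change to day 180 or the average over follow-up. Show the change from the other baseline as sensitivity. Four instruments still leave four contrasts, so report estimates with intervals and keep them labelled descriptive.
- One likelihood-based repeated-measures model per score, using all surveys, with time as a category. Keep the covariance simple: a random intercept, plus a patient-by-period (before/after conversion) effect if it can be fitted. Use small-sample or patient-level jackknife standard errors. If the period effect cannot be fitted, prefer the jackknife: under structure B, Kenward-Roger without that effect gave a type I error of 6.2-8.4%, against 3.7-5.7% for the jackknife across all structures.
- Numbers observed at each visit, and the paired result alongside.
- A sensitivity analysis shifting unobserved scores by stated amounts. For a day-180 contrast with 40% missing, each 1-point shift moves the mean change by 0.4 × 1 = 0.4 points.

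Report the surveys of the 15-20 already converted patients descriptively, without a pre/post contrast. For utilization, compare rates per unit time.

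Cost: a paragraph of SAP text, slightly more analysis work and an explicit missing-at-random assumption. No new data are needed.
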